- Disordered eating, as evidenced by meeting criteria for Anorexia Nervosa, Bulimia Nervosa, Binge Eating Disorder, Other Specified Eating Disorder, Unspecified Eating Disorder, or Avoidant Restrictive Eating Disorder during the SCID-5 interview at baseline testing.
- Substantial imminent risk of suicide as assessed during the SCID-5 interview.
- Body mass index (BMI) < 20 kg/m²
- Habitual consumption of a structured low-carbohydrate diet in the last 6-months
- Gastrointestinal disorders or allergies that would prevent adherence to prescribed diets
- Alcohol consumption in excess of 3 drinks/daily or 14 drinks/weekly
- Diagnosed diabetes, liver, kidney, or other metabolic or endocrine dysfunction, or use of diabetic medications other than metformin
- Inability to access or prepare appropriate KD foods/meals
- Pregnant, lactating, or planning on becoming pregnant during the study
- Unwilling to perform finger-stick blood testing or continuous glucose/ketone monitoring

Exclusion for optional MRI:

- The CCBBI screening form (<https://redcap.osumc.edu/redcap/surveys/?s=N3XJ4WC7T9>) will be used to assess MRI eligibility. Endorsement of items that contraindicate MRI will serve as exclusion criteria (pacemaker, stint, claustrophobia, etc.).

Recruitment:

OSU students will be recruited through the Office of Student Life's CCS, and through the recommendations of the 50+ counselors associated with the Health and Wellness Center who are

charged with the care and wellbeing of OSU students experiencing major depressive symptoms. All potential participants must be currently enrolled with the Student Life’s CCS. Initial screenings for qualifying inclusion and exclusion criteria will be conducted by [name] and his team. We expect to enroll between 30 and 60 participants. The total number of students who received clinical services through CCS during the 2020-2021 academic year was 5,488. Thus, recruiting 30 – 60 participants who meet inclusion and exclusion criteria is an achievable goal.

METHODS

Study overview:

[figure not shown]

Fig. 1 Experimental Approach.
Created with BioRender.com

Study Procedures

The timeline of various study procedures is detailed in **Table 1**.

Table 1: Study Assessment Timeline

Test	Week												
	BL	1	2	3	4	5	6	7	8	9	10	11	12
SCID-5 RV ¹	X												
WHO-5 ²	X		X		X		X		X		X		X
PHQ-9 ³	X		X		X		X		X		X		X
Depression Scale ⁴	X						X						X
CGM/CKM ⁵	X	X				X	X					X	X
Finger Stick BHB ⁶	X	X	X	X	X	X	X	X	X	X	X	X	X

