Survey/Side Effects ⁷	X						X						X
Venous Blood Draw ⁸	X						X						X
Body Composition ⁹	X						X						X
Blood Pressure ¹⁰	X						X						X
Cognitive Testing ¹¹	X												X
MRI ¹²	X												X

1. SCID-5 RV: Structured Clinical Interviews will be used at baseline after Informed Consent to determine if participants are eligible to continue with the study's dietary intervention.

2. WHO-5: The WHO-5 is a short 5 item questionnaire that will be used bi-weekly to assess participants psychological well-being. This questionnaire will be administered digitally via RedCap or Qualtrics.

3. PHQ-9: The Patient Health Questionnaire-9 will be used bi-weekly to assess each participant's degree of depression (i.e., intensity and severity). This questionnaire will be administered digitally via RedCap or Qualtrics.

4. Depression Scale: The Hamilton Rating Scale for Depression is a questionnaire that will be given to participants and BL, week-6 and -12 of the intervention to evaluate improvements in depression symptoms.

5. CGM/CKM: Continuous Glucose/Ketone Monitors will be applied after Informed Consent. The sensor will be checked by the study team at each test day and will be removed and replaced by a fresh sensor at ~6-week intervals during the study. The sensor will be removed at the end of the final test day

6. Finger Stick BHB: Finger sticks will be taken daily in the morning, by the participant to determine ketone and glucose levels at a fasted state. Measurements will be reported daily in RedCap or Qualtrics.

7. Surveys/ Side Effects: Participants will complete the Automated Self-administered 24-hour Dietary Assessment Tool (ASA24[®]) at baseline. They will also complete behavioral and cognitive surveys during each testing day.

8. Venous Blood Draw: A fasting blood draw will be taken from the antecubital vein during each testing day.

9. Body Composition: Anthropometric data will include: Lean Body Mass by DXA, BMI, height and weight.

10. Blood Pressure: This will be determined by manual cuff and recorded by research staff.

Participants will wear a Bluetooth heart rate monitor chest strap throughout the test day.

11. Cognitive Testing: Cognitive tests will be conducted via iPad to provide measures of global cognition and specific cognitive domains.

12. MRI: Structural and Functional MR imaging will be done to assess changes in cortical thickness, brain volume, and functional connectivity.

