Pre-Study Screening: Students with depression who are currently engaged with counseling treatment provided through the CCS, will be made aware of the study during their therapy sessions. Potential participants will be provided with a research flier by their CCS therapist. If the potential participant takes interest in the study, they will complete a pre-screening checklist which includes a brief summary of the study and a series of inclusion/exclusion criteria to which they will answer ‘yes’ or ‘no’. If the potential participant passes this pre-screening checklist, they will be scheduled to meet with study staff for an informed consent meeting to thoroughly discuss the study, review informed consent and HIPAA information. Upon consent, the participant will then meet with study team for eligibility determination.

Informed Consent and Eligibility Determination. Participants will review the informed consent and HIPAA information with study personnel. After providing consent, participants will complete clinical interviews and questionnaires, which may involve inquiry about personal information, including demographics, medical history, health behaviors, and current medications. These questions will ensure inclusion eligibility. Participants who meet eligibility criteria will be fitted with a Continuous Glucose and Ketone Monitor (CGM/CKM) and scheduled for their dietary and cognitive assessment appointment. MRI scanning will be an option for participants who are interested and eligible for MRI. Those interested in participating in the MRI sessions will complete the CCBBI MRI eligibility screening form and scheduled for MR imaging with study team. The schedule of study testing visits is shown in **Table 2**.

Table 2: Scheduled Study Visits

Week	Appointment #	Description	Expected Time Frame
Baseline	1	Determine potential participant interest in the study and go over pre-study eligibility form with CCS team member. A pamphlet describing the dietary protocol will be handed out at this time.	1 hr
Baseline	2a	Informed Consent Form & Structured Clinical Interview	90 min
If participant is ineligible or no longer interested, they are compensated, and study participation is terminated. If eligible and interested, participant continues in study as below:			
Baseline	2b	Mental Health Battery and Continuous Glucose Monitor / Continuous Ketone Monitor application	90 min

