Baseline	3a	Weight, Hydration Status, Body Composition Testing, Survey/Side Effects, Venous Blood Draw, Body Composition, and Blood Pressure.	1 hr
Baseline	3b	Cognitive testing	1 hr
Baseline	3c	Dietary consult	45 min
Baseline	3d*	MR Testing	1 hr

5	4	Continuous Glucose Monitor / Continuous Ketone Monitor application	5 min
6	5	Weight, Hydration Status, Body Composition Testing, Survey/Side Effects, Venous Blood Draw, and Blood Pressure.	1 hr
11	6	Continuous Glucose Monitor / Continuous Ketone Monitor application	5 min
12	7a	Cognitive Tests	1 hr
12	7b	Weight, Hydration Status, Body Composition Testing, Survey/Side Effects, Venous Blood Draw, and Blood Pressure.	1 hr
12	7c*	MR Testing	1 hr

Testing Visits. As detailed in Tables 1 and 2, PHQ-9 data will be collected at baseline and bi-weekly by means of an internet-based survey and questionnaire administration program (REDCap / Qualtrics). HRSD data will be collected in-person or virtually by study assessors at baseline, 6- and 12-weeks. As part of their standard counseling protocol, counselors will also administer the CCAPS-34 to assess global mental health at baseline and 3-wk intervals. Other outcomes will be assessed at baseline, 6- and 12-weeks at a single visit in the PAES Building centrally located on the OSU campus (see **Fig 1**).

For testing at the PAES (**Fig 2**), subjects will arrive to the lab in the morning after an overnight fast. We will test for hydration, measure height and body mass, and then have participants complete surveys followed by resting blood pressure. A phlebotomist will obtain blood samples from a forearm vein in subjects after sitting for 10-min. Appropriate sample tubes will be used for EDTA, sodium heparin, or serum for different analytes. A serum tube will be sent to Quest Diagnostics to assess standard chemistry panel (liver enzymes, kidney function, lipids, etc.).

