Serum and plasma will be immediately centrifuged and aliquoted into tubes and stored at -80°C until subsequent analyses. Samples will be thawed only once for analysis and assayed in duplicate for ketones, glucose, and insulin, which will be used to calculate an index of insulin resistance, and HbA1c. Extra serum and plasma will be archived for future analysis of biomarkers that may provide insight into novel associations with depression. We will determine body composition from a single whole-body scan using dual-energy x-ray absorptiometry (iDXA, Lunar Corporation, Madison, WI). Finally, subjects will complete a battery of computerized cognitive tests. Total time for this visit will be less than 2-hours.

[figure not shown]
[figure not shown]

Fig. 2 test day timeline. Created with BioRender.com

Neurocognitive test materials and procedure. Testing sessions will be administered by trained lab staff. All participants will complete an assessment of cognitive function with the NIH Toolbox (IPAD-based assessments that examines cognitive function) and standardized neuropsychological testing (such as sub-tests from the Delis-Kaplan Executive Function System, Stroop Color Word Test, and Wechsler Memory Scale). Computer-based testing of memory (pictures and words) and executive function (attending to visually presented stimuli, such as scenes) may also be administered.

The gradCPT contains grayscale photographs of mountain scenes and city scenes. Scene images gradually transition from one image to the next^{31,32}). Participants are instructed to press the space bar on the keyboard for each city scene, and to withhold responses for mountain scenes. Practice trials will be given prior to the start of the task with feedback for each trial response to ensure that the task instructions were understood. The actual task lasts approximately 4 minutes and feedback is not provided during the task.

A. Illustration of gradCPT. Scenes gradually transition from one image to the next image. Participants are instructed to respond to city scenes and withhold for mountain scenes (Esterman et al., 2012).

MRI Image Acquisition (approximately 60 min). Participants who are MRI-eligible may volunteer for pre- and post-intervention MRI. We have the resources to complete pre- and post- intervention

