The Investigator is responsible for ensuring that participants' anonymity will be maintained. For all the data collected over the course of the study for each participant (i.e., records, biological samples and questionnaires) a unique subject identifier (i.e., a code) will be assigned and used instead of the subject's name. The code for each participant which links the subject name with their identifier will only be available to research personnel. Electronic CRFs or other documents will identify participants by initials, number, or code, and not by name. The Investigator will keep a separate log showing codes, names, and addresses. Any records that contain the subject's name and identifier will either be stored in the Clinical Psychology file storage room in a file cabinet (locked) or protected on a computer via password protection on the individual digital file and password protection on the computer the file(s) are stored on. All other records that contain the

subject identifier only will also be kept in either a file cabinet in our locked file storage room or on a password protected computer. Biological samples collected from each participant will be kept in a storage freezer labelled only with the subject identifier. Subject names will never be used in any presentation or publication resulting from this study. The records will be maintained until the data are published and up to a maximum of ten years after the completion of the study. All records or biological data obtained after signing of the informed consent (including the screening visit, even for subjects that are not eligible for participation in the study) are treated with the same confidentiality safety measures as those subjects who qualify. Any information obtained during the prescreening for participants that were not eligible will be deleted. [Any potential incidental findings from MRI, blood biomarkers, etc. will be shared with the participant. Incidental findings from the MRI imaging will be reported to the participants primary care physician within 30 days of finding. The remaining information \(ie. Blood biomarkers\) is non-diagnostic and will be provided so the participant may choose to share with their physician.](#)

5. Withdrawal of Participants from the Study

Participants may be removed from the study for any of the following reasons:

- A participant requests discontinuation;
- The Investigator initiates removal for medical or compliance reasons;

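### The protocol calls blood results non-diagnostic, which is wrong for its clinical chemistry panel, and states no study review of that panel, even before the diet starts

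*Protocol*

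**What the plan says.** Under Conduct of the Study, item 4 (Participant Confidentiality), the protocol states: "Any potential incidental findings from MRI, blood biomarkers, etc. will be shared with the participant". MRI findings then go to the primary care physician within 30 days. The remaining information, with blood biomarkers given as the example, "is non-diagnostic and will be provided so the participant may choose to share with their physician". No time limit is attached to blood results.

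The blood tests are described under Testing Visits. One part is a clinical laboratory test: "A serum tube will be sent to Quest Diagnostics to assess standard chemistry panel (liver enzymes, kidney function, lipids, etc". The other part is stored: "Serum and plasma will be immediately centrifuged and aliquoted into tubes and stored at -80°C until subsequent analyses". Ketones, glucose, insulin and HbA1c are listed with these later assays. The note to Table 1 says: "A fasting blood draw will be taken from the antecubital vein during each testing day", and the table marks baseline, week 6 and week 12.

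On entry, the Exclusion Criteria list "Diagnosed diabetes, liver, kidney, or other metabolic or endocrine dysfunction". The section on informed consent and eligibility relies on interviews and questionnaires that cover medical history and current medications: "These questions will ensure inclusion eligibility".

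**The concern.** A chemistry panel from a clinical laboratory is an ordinary clinical test, and its liver and kidney results can call for medical follow-up. A blanket statement that blood results are not diagnostic misdescribes it. The protocol then uses that description as the reason for leaving it to the participant whether any physician hears of the result.

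The baseline panel matters most. A liver or kidney problem that nobody has yet diagnosed could first show up there, just before 12 weeks on a diet that changes electrolyte intake. If the protocol is followed as written, a flagged value can reach the participant described as non-diagnostic while no one on the study is required to look at it before the diet begins. This is a participant-safety point. It does not bear on the estimate of change in depression scores.

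**Working it through.** No arithmetic applies. The check sets the relevant sections side by side.

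1. **What the label covers.** Participant Confidentiality applies it to blood biomarkers without separating types. Testing Visits describes two: a standard panel sent to an outside clinical laboratory, and assays run later from frozen aliquots. The label can fit the second type. It does not fit the first, whose contents are routine clinical measures of organ function.

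2. **HbA1c.** It is listed with the stored-sample assays, but it bears on the diabetes exclusion. The protocol does not say whether it counts as a research assay or as a clinical result, so the line between the two types is unsettled at this point.

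3. **Who is told, and when.** The Incidental Findings section provides for contact with the physician within 30 days for MRI, cognitive and fitness assessments. It does not name blood. Participant Confidentiality gives the same 30 days for MRI findings only. The two sections therefore agree in setting no physician contact and no time limit for blood.

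4. **Order of events at baseline.** In Table 2, consent and the structured clinical interview form visit 2a. The decision row follows directly: "If eligible and interested, participant continues in study as below". The venous draw first appears at visit 3a. Eligibility is thus decided before any panel exists.

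5. **Start of the diet.** The Dietary Intervention section makes the start conditional on baseline testing having been completed. A test is complete when the blood is drawn; the section does not say that the laboratory report must have been returned or read.

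6. **What could act on a flagged value.** Item 5 (Withdrawal of Participants from the Study) lets the investigator remove a participant for medical reasons, or for an adverse event or condition that puts the participant at undue risk. That provision could deal with a flagged panel. No section names a person to read the panel or links a flagged value to this decision.

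7. **Why liver and kidney values are relevant here.** The protocol excludes people with diagnosed dysfunction of these organs. The diet calls for slightly higher sodium and potassium to replace what natriuresis removes, with magnesium and calcium supplements for muscle cramping. The changes are modest and have a stated purpose, but they make kidney function worth reading before the start.

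**The case against.** The strongest case on the other side is that the protocol is silent rather than negligent. Sharing incidental blood findings presupposes that someone identifies them. Staff may well read every panel, and the consent form, which is not at hand, may describe the return of results. All of that is possible. A reader might infer from the text that nobody reviews the panels or that abnormal results are withheld. The documents support neither: results are to be shared, and the most that can be said of review is that none is stated.

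A reader might also infer that the protocol breaches its own entry rule. It does not. The exclusion concerns diagnosed disease, screening by history and medication is a coherent choice, and the panel components are listed as outcomes, not as eligibility tests.

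Nor does the text support calling the diet's electrolyte changes a hazard in themselves, since the higher intakes are slight and replace losses. Other monitoring also exists: daily fasting glucose and ketone readings reported to the study, sensor checks on test days, and side-effect surveys and blood pressure at baseline, week 6 and week 12. None of it shows liver or kidney function.

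Finally, leaving disclosure to the participant is defensible for students in counseling, for whom privacy has real weight. That stands, and it is why direct contact with an outside provider should not be required here. It does not answer the main point. Privacy is a reason not to write to an outside physician; it is no reason for the study to leave its own panel unread or to describe it wrongly to the person who receives it.

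**Conclusion.** The concern holds in a limited form. The non-diagnostic label is wrong for the standard chemistry panel, and the text at hand states no study review of that panel, including before the diet starts. This goes beyond missing detail, because the protocol makes a positive choice about blood results and gives a reason that does not fit one of its own tests.

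Its size cannot be put in numbers. The protocol gives no rate of abnormal panels in this age group. A reader might be tempted to count the weeks of diet remaining after each draw as time at risk. Those weeks describe only the length of the study and say nothing about harm.

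The conclusion assumes that the blood-biomarker wording includes the chemistry panel, which is the natural reading of a sentence covering everything other than MRI findings, and that no document outside the text at hand already assigns the review. If either assumption fails, the remedy reduces to a clarifying sentence. The efficacy analysis is unaffected either way. The change is a cheap improvement that should be made.

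**What to change.** Amend Participant Confidentiality, and cross-refer from Dietary Intervention and from the withdrawal section, as follows:

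- Limit the non-diagnostic label to research assays run later from stored samples, and say whether HbA1c is one of them.
- Have the investigator, or an existing clinician whom the investigator designates, check laboratory-flagged chemistry values on receipt, with the baseline panel checked before the diet starts.
- Tell the participant promptly when a flagged value needs medical follow-up.
- Apply the existing provision for removal on medical grounds or undue risk where the value calls for it.

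Direct contact with the participant's outside provider can remain optional. It is a privacy trade-off, and this fix does not depend on it.

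The cost is a few minutes of review per panel and a possible short delay to the diet while the baseline result is awaited. No new test or visit is needed, because the blood is already drawn and sent.

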Primary Outcomes. Adherence will be determined by the number of participants completing the 12-week intervention. We expect >80% of enrolled participants to complete the 12-week trial. Additionally, we will determine the number of participants who consistently maintain a level of nutritional ketosis (average ketones ≥ 0.5 mM).

The primary efficacy outcome will be depression score as assessed by PHQ-9 and HRSD. The self-reported PHQ-9 is a measure of depression symptom severity. It maps onto DSM-5 criteria for Major Depressive Disorder and is widely used in both clinical and nutrition research settings. The HRSD is an observer-rated measure of depression mostly used in research settings; the HRSD will be used to provide objective and standardized ratings of symptom severity, including ratings

that require external observation such as psychomotor retardation. The PHQ-9 and HRSD will be administered bi-weekly to provide a trajectory of depression symptoms.

Secondary Outcomes. In addition to changes in symptoms of depression, we will assess changes in a number of metabolic markers and cognitive markers of psychological health. We will assess the following to quantify these changes: Body weight, body composition, blood pressure, glucose, insulin, HbA1c, chemistry panel, lipids, and cognitive measures, structural and functional brain MRI). To examine changes in inflammation, we will assess the following markers: interleukin 1, interleukin 6, C-reactive protein, tumor necrosis factor-alpha, and WBC count with differential.

PARTICIPANTS

We expect to enroll up to 60 young adults with major depression into a KD intervention over a 12-week period. Participants will be able to pick up study fliers or will be handed fliers by CCS team members. Study fliers will include all inclusion and exclusion criteria and will provide potential participants with research team contact information. Participants must meet all inclusion criteria and none of the exclusion criteria as indicated on a prescreening checklist before baseline testing. Pre-screening and BL inclusion/exclusion criteria is outlined below.

Inclusion Criteria:

- OSU students (age 18-30 years at the time of enrollment) with confirmed major depressive disorder as determined by SCID-5 diagnosis at baseline testing.
- Currently engaged in counseling treatment for depression at CCS
- Available for a 12-week period and indicate willingness and ability to eat KD foods as prescribed

Exclusion Criteria:

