Patient demographic and characteristics information, pre- and post-intervention depression scores and other outcomes will be summarized for the KD group at every time point. Considering this is a pilot feasibility study, we will focus on calculating effect sizes. Changes in depression scores within the KD group will also be evaluated using a linear mixed model for repeated measures, with the baseline score potentially included as a covariate to control for baseline variability. The linear mixed models (Multi-level Model, MLM) will allow us to easily handle missing data (assuming Missing-at-random) and estimate within group effects from the same model. These models can also easily handle co-variates and are robust to violations of normality. Normality and heteroscedasticity will be checked using residual plots. All data that are non-normal may be either suitably transformed (e.g., log, Box-Cox) or analyzed using non-parametric methods (Kruskal-Wallis test).

Incidental Findings

There may be incidental findings observed on MRI, cognitive, and fitness assessments. For each type of assessment, the participant’s primary care physician will be contacted within 30 days of incidental finding detection. Each participant will provide contact information for their healthcare provider at entry of the study.

STUDY MONITOTRING

Concomitant Medication/Supplements and Treatment

All concomitant medications/supplements used 1 month prior to Screening Visit and during the study will be reported to the study personnel for assessment and recorded in the participant’s study documents.

CONDUCT OF THE STUDY

1. Ethics and Regulatory Considerations

This study will be conducted according to Good Clinical Practice Guidelines, the Declaration of Helsinki (2004) and United State Code of Federal Regulation Title 21. Signed written informed consent for participation in the study will be obtained from all participants before protocol-specific procedures are carried out. Participants will be informed of their right to withdraw from the study at any time. Participants will be informed that their participation in the study is completely voluntary, personal information will be both de-identified to preserve anonymity.

2. Institutional Review Board

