- Occurrence of any AE or condition that could, in the Investigator's opinion, interfere with the evaluation of the effect of the study beverage or put the participant at undue risk.

It is understood by all concerned that an excessive rate of withdrawals can render the study uninterpretable, therefore, unnecessary withdrawal of participants should be avoided. Should a participant decide to withdraw, all efforts will be made to complete and report observations as thoroughly as possible. In the event that a participant is withdrawn from the study, the reason for the withdrawal will be documented.

Reference List

1. Organization WH. Depression. [Online]. 2021; <https://www.who.int/news-room/fact-sheets/detail/depression>. . Accessed October 22, 2021.
3. Rosner RI. Making a Case for Interpersonal Psychotherapy. *PsycCRITIQUES*. 2012;57(41).
6. Phillips MC. Metabolic Strategies in Healthcare: A New Era. *Aging and Disease*. 2021:0-

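### Undefined removal for non-compliance feeds the completion outcome and may end depression scoring in the participants who left the diet, because follow-up is promised only for those who withdraw themselves

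*Protocol*

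**What the plan says.** Protocol, Outcomes (Primary Outcomes): "Adherence will be determined by the number of participants completing the 12-week intervention". The expectation attached to it is "We expect >80% of enrolled participants to complete the 12-week trial". Under the same heading, "we will determine the number of participants who consistently maintain a level of nutritional ketosis (average ketones ≥ 0.5 mM"), with no denominator given. Efficacy is also primary: "The primary efficacy outcome will be depression score as assessed by PHQ-9 and HRSD".

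Protocol, Conduct of the Study, item 5 (Withdrawal of Participants from the Study): participants may be removed from the study at their own request, because of an adverse event or other condition, or where "The Investigator initiates removal for medical or compliance reasons". No definition or threshold for compliance is given. The section then says "Should a participant decide to withdraw, all efforts will be made to complete and report observations as thoroughly as possible". For a participant who is withdrawn by others, it requires only that the reason be recorded. It also asks that unnecessary withdrawals be avoided.

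Protocol, Data Analysis and Statistical Methods: change in depression scores is analysed with a linear mixed model that "will allow us to easily handle missing data (assuming Missing-at-random"). Covariates are allowed in general terms; ketone or diet data are not named.

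**The concern.** Two things collide. First, the trial sets out to measure whether students can keep to the diet for 12 weeks, but not keeping to it is a permitted reason for staff to end participation. Ketone readings are self-reported daily, so staff would have the information to act on. The completion rate would then reflect both what participants did and how strictly staff applied an unwritten rule.

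Second, removal is from the study, not only from the diet, and the commitment to go on collecting data does not extend to investigator-initiated removal. The background section, just before Impact, reports that in an earlier diabetes cohort improvement in depressive symptoms was correlated with the degree of carbohydrate restriction and ketosis. If that carries over, later scores would be lost mainly from people expected to improve least.

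The stakes are the pilot's main product. Impact says the data will supply effect-size estimates for a comparative trial. An estimate tilted toward those who kept to the diet could leave that trial too small.

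**Working it through.** The protocol gives no removal rate, score change or SD, and does not derive its expectation of more than 80% completion. There is therefore no plan figure to reproduce. All rates and score changes below are assumptions; only the sample size (30 to 60), the visit schedule, the enrolled denominator and the type of model come from the protocol.

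**Completion.** More than 80% means at least 49 of 60 or 25 of 30. Assume 60 enrolled, 6 voluntary dropouts, and that anyone removed would otherwise have completed. Completion = (60 − 6 − removed)/60:

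| Removed for non-compliance | Completion over enrolled |
|---|---|
| 0 | 54/60 = 90% |
| 3 | 51/60 = 85% |
| 6 | 48/60 = 80% |
| 12 | 42/60 = 70% |

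The rate moves by 20 percentage points on staff decisions alone, and six removals are enough to miss the expectation. The movement is downward.

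**Ketosis.** Assume 30 of the 60 average at least 0.5 mM and all 30 complete. Over enrolled the result is 30/60 = 50% whatever the number removed. Over completers it is 30/54 = 55.6% with none removed, 30/48 = 62.5% with 6 and 30/42 = 71.4% with 12. Inflation needs a completer denominator.

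**Depression.** Assume a 12-week change of −8 points in compliers and −4 in non-compliers, a baseline mean of 15 (SD 4), individual variation in 12-week change of SD 2, residual SD 2.5, and scores every two weeks. All non-compliers are removed after week 2, 4 or 6, with no later scores.

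- True change in all enrolled = (1 − p)(−8) + p(−4), which is −7.6, −7.2 and −6.8 for p = 10%, 20% and 30%.
- The missing-at-random estimate is the maximum-likelihood mean of an unstructured repeated-measures model. With one removal time it has a closed form: regress the week-12 score on the earlier scores in those who stay, then predict at the mean of the earlier scores in everyone. It was run on 400,000 simulated participants per setting so that sampling error is negligible.

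| Removed | True change | Mixed-model estimate (removal after week 2 / 4 / 6) | Overstatement |
|---|---|---|---|
| 10% | −7.6 | −7.96 / −7.93 / −7.87 | 0.3 to 0.4 |
| 20% | −7.2 | −7.94 / −7.84 / −7.75 | 0.6 to 0.7 |
| 30% | −6.8 | −7.90 / −7.78 / −7.63 | 0.8 to 1.1 |

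The completer mean is −8.0 throughout, an overstatement of 4p = 0.4, 0.8 and 1.2 points. The mixed model does better because it uses scores from before removal, but about 70% or more of the completer bias remains (at 30% removed after week 6: about 0.84/1.2 = 70%). If compliers and non-compliers change equally, the overstatement is zero.

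**The case against.** The strongest reply is that the protocol already contains safeguards. Removal is permitted, not required; unnecessary withdrawals are discouraged; reasons are recorded, so compliance removals can be identified and reported; the mixed model keeps every score collected before removal; and covariates may be added. Compliance might mean missed visits or unreturned questionnaires rather than diet. All of this stands. It is why the estimate may be biased, and why one cannot say that it is.

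A reader might go further in four ways that the document does not support.

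- That the adherence rate is inflated. The stated expectation is for enrolled participants, so a removed participant is a non-completer and the rate falls.
- That the ketosis result is inflated. The protocol defines a count and states no denominator; only reporting among those remaining would raise it.
- That removal stops data collection. The protocol is silent on this. Follow-up after investigator removal is not promised, which is not the same as being ruled out.
- That the people removed are those for whom the diet fails. The protocol does not equate non-compliance with non-response; its background only makes a link plausible.

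The safeguards do not close the gap. Recording a reason does not replace a score, and an analysis plan, however good, cannot recover scores that were never collected.

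**Conclusion.** The point holds in a limited form. An undefined, discretionary removal rule bears on a primary outcome defined as completion, and the follow-up commitment as worded omits the participants removed under that rule. Completion is therefore partly an investigator decision, with removals lowering it over all enrolled. The depression improvement may be overstated: in the illustration by about 0.6 to 0.7 points at 20% removed, against a true change of 7.2. That size rests on an assumed 4-point difference between compliers and non-compliers, on removal of all non-compliers by week 6, and on no scores being collected afterwards. With few removals, continued assessment, or no relation between compliance and change, it shrinks to nothing. This is a cheap improvement to the protocol, not an error that invalidates the design.

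**What to change.** Reconcile Primary Outcomes with item 5 of Conduct of the Study:

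1. State that non-compliance with the diet does not by itself end outcome assessment, and say what compliance refers to in the removal rule.
2. Extend the commitment to complete observations to investigator-initiated removal. The bi-weekly online PHQ-9 and the week-6 and week-12 HRSD of Table 1 continue unless the participant withdraws consent to them.
3. Count completion and ketosis over all enrolled, with removed participants as non-adherent, and report the number removed for compliance reasons separately.
4. Keep all scores from removed participants, before and after removal, in the main mixed model.

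Medical removal and decisions on whether someone continues the diet are left as they are.

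The cost is some protocol wording and a few more remote assessments: PHQ-9 is already online and HRSD may be done virtually. The effect size may come out smaller, but it would describe everyone who started the diet.
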